If the patient has two or more decubitus lesions at the same stage, the doctor will choose to treat the lesion of which, in his opinion, the data acquisition (photography and size measurement) is better. If a patient has two or more lesions of different stages, the doctor will decide to include in the study only one of them, based on the number of lesions inserted at that time in the two groups, choosing the group with a smaller number: In this way, attempts are made to ensure a numerical trend as simultaneous as possible in the two groups of lesions (e.g. if the number of 2°stage lesions enlisted is less than the number of 3°stage lesions enlisted, then the 2°stage lesion will be included in the study). In the case of a numerical parity of the two groups of lesions, the doctor will decide to treat the lesion with a position that allows a better data acquisition (photographic image, measurement, etc.).

Case Report Forms

Case Report Forms are unique to every patient. It will be used the form of injury assessment already present at the Investigator Centre; the data collection by the Principal Investigator includes: patient's name and surname, date of birth, room number, medical record number, date of surgery, any allergies and the characteristics of the lesion under investigation -position and degree of the lesion-. Another section dedicated to the characteristics of the lesion, includes: dimensions (length x width), the amount of exudate and the type of tissue. All these features will be evaluated, according to the criteria of the international scale PUSH, with a score, specified in the legend in the form, of which the total will be reported at each visit.

The Pressure Ulcer Scale for Healing (PUSH) is a tool designed by the National Pressure Ulcer

Advisory Panel (NPUAP) and used to observe the trend of pressure ulcers over time, classifying them regarding the area of extension, the exudate and the tissue type, noting the partial score for each characteristic of the ulcer and summing those scores to obtain the total. Comparing the relevant total scores over time will provide an indication of the improvement or worsening of the healing of the pressure ulcer.

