During the 4 weeks of observation, once a week, concomitantly with the visit, and during the last visit (V12), a photographic image of the wound will be collected in order to be able to assess both qualitatively and quantitatively the progress of healing. The images will be collected with a portable device suitable for taking photographs (eg. tablet).

The acquisition of the photographic image will take place after any cleansing / debridement of the wound, before treatment with EmoLED / bandage.

Each photograph will be named with the patient code and the date of the visit. The photo shall cover

the entire area of the lesion. Next to the lesion will be placed a special ruler for the measurement of the area of the lesion.

Guidelines for photos' standardization

In order to have accurate measurements it is necessary that the image registration procedure is standardized.

The wound must be well focused and framed frontally; in all the photos the ruler with the patient's identification code must appear and the date and must be in focus so as to have the 1 mm scale reference. The operator should try to take the picture by fully framing the wound (preferably considering a margin around the wound), and position themselves so that the ruler is always present in the frame.

It is also advisable to avoid artifacts from the movement of the subject or operator, as they cause blurring and therefore make it difficult to correctly view the ruler or the wound.

Bias

The staff participating in the study will be trained on the correct use of the device and accessories, as well as on the correct execution of the clinical protocol and on the compilation of the associated forms.

The EMOLED staff is always at the team's disposal for any clarification or doubt during the study.

In order to avoid bias during the procedure for the assignment of the patients enrolled to the experimentation group, it should be noted that the randomization grid is not distributed to the investigators: instead, opaque and sealed envelopes are distributed that inside have an adhesive label with the patient's ID and their attribution group that reflects the randomization grid. This adhesive label must be glued on the patient folder containing the informed consent and the Case Report Form.

Since this is an experiment with a medical device that emits blue light, in this case the masking of the assignment to one of the two groups cannot be carried out.

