Being diabetes a condition that affects the timing of wound healing, and being widely distributed in the population under study, enlisted patients will also be randomized for this factor, so that the two treatment groups can be homogeneous.

The randomization grid is generated with the on-line software available on the website "randomization.com".

The 2° stage and 3° stage lesions are randomized separately, as well as diabetic and non-diabetic patients.

It is a 1:1 randomization, stratified, with 4 blocks of 10 patients distributed in the two groups (treated and control).

Patient selection

All patients under treatment who meet all the inclusion criteria listed below will be considered for

inclusion in this study. Patients will be evaluated using a standard procedure that includes the collection of the medical history and a physical examination of the patient.

Inclusion Criteria

- Patients with 2° or 3° stage lower limb/ sacrum located pressure ulcers;
- Patients with 2° or 3° stage pressure ulcers with a $\geq 2\text{cm}^2$ lesion area;
- Patients with a hospitalization waiting time < 30 day;
- Men and women aged ≥ 50 years;
- Patients with a Braden scale score ≥ 11 ;

Exclusion criteria

- Patients who are participating in other clinical trials with drug or medical device;
- Patients with third stage pressure lesions, on the lower limbs or on the sacrum, with undermining wounds, tunneling or eschar;
- Patients with systemic or superficial infection at the time of recruitment, that need systemic antibiotic therapy;
- Patients with a history of self-harm who can voluntarily alter the course of healing;
- Patients under intravenous therapy with doses of corticosteroids above 40mg/day;
- Patients under immunosuppressant or cytostatic drugs therapy;
- Women who are pregnant or breastfeeding¹;
- Patients with neoplasia;
- Patients with pathologies that induce skin photosensitivity;
- Patients with a life expectancy of less than 30 days.

In order to be eligible for the planned treatment phase, all the inclusion and exclusion criteria must be met. Any concomitant pharmacological therapy must be maintained.

Number of patients expected to enroll

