A total of 40 "evaluable" patients will be recruited in total, 20 patients with second stage PU and 20 patients with third stage PU, 10 per arm (Treated and Controlled) within each group, at the facility involved in this Clinical Study. By "evaluable" patient it is meant a patient enrolled who has respected the temporal sequence of treatments as indicated in this protocol. The expected time for enrollment is 10 months. However, the study will continue until the number of patients required by this protocol is reached.

Enrollment point

Once the patient has signed the Informed Consent, the Principal Investigator enters the data in the Enrollment Register, scrupulously checking all the inclusion and exclusion criteria; if all the criteria

are met, the patient is considered enrolled in the clinical trial and subsequently randomized.

Number of experimental medical devices expected to be used

Each experimental site will be equipped with a v.1 EmoLED medical device.

Time-frame of the study

The Study has an indicative duration of 12 months with an expected enrollment period of 10 months. The study, however, will continue until the number of patients required by this protocol is reached.

¹ The state of pregnancy or breastfeeding will be certified on the basis of the patient's declaration.

Medical and surgical procedures and study follow-up

The Control Group will follow the standard treatment indicated three times a week for the 4 weeks of observation. The experimental group will undergo, in addition to the standard treatment, treatment with Emoled three times a week for 4 consecutive weeks.

This treatment consists of irradiation with the blue light emitted by the device for one minute on the injured area. If the lesion has a greater extension than the irradiated area, multiple repeated applications will be performed, on adjacent areas, until the entire area is covered.

The treatment with EmoLED will be carried out in correspondence with the dressing change of the lesion.

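### The protocol prints a fixed block size of 10 for an unmasked single-facility trial, so staff who tally allocations can deduce some of the next ones (about 4 to 7 of 40) despite sealed envelopes

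*Combined protocol and SAP*

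**What the plan says.** The Bias section gives the scheme: "It is a 1:1 randomization, stratified, with 4 blocks of 10 patients distributed in the two groups (treated and control". It adds that "The 2° stage and 3° stage lesions are randomized separately, as well as diabetic and non-diabetic patients", which makes four strata (two stages by diabetes yes or no). The section on the number of patients sets the target at "20 patients with second stage PU and 20 patients with third stage PU, 10 per arm (Treated and Controlled) within each group", all at one facility.

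The safeguard is that "the randomization grid is not distributed to the investigators: instead, opaque and sealed envelopes are distributed". The label from the envelope, which shows the group, is then stuck on the patient folder. On blinding, the same section says that "the masking of the assignment to one of the two groups cannot be carried out".

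Under Ethical considerations, the investigator must run the study according to the protocol. Under Recording of clinical data, when a patient has several lesions of one stage, "the doctor will choose to treat the lesion of which, in his opinion, the data acquisition" is better. When the stages differ, the stage with fewer lesions entered so far is taken; at parity, the doctor picks the lesion whose position allows better data acquisition.

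**The concern.** Withholding the list and sealing the envelopes protects only what cannot be worked out. Here the staff see every past allocation and work from a document that states the block size. Anyone who keeps a count per stratum can tell when one arm of a block is full, and from then on knows the next assignments.

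For this to bias the comparison, someone must act on the knowledge, by timing an enrolment or by choosing a lesion with a better or worse outlook. With 10 patients per arm within a stage, one steered patient is 10% of an arm. The results are also meant to inform the sample size of later studies.

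**Working it through.** **Inputs.** From the Bias section: 1:1, 4 blocks of 10, four strata. From the patient-number section: 40 evaluable patients, 20 per stage, 10 per arm within each stage. From Statistics: about 25% drop-out. The diabetic share is not given; 20% to 50% is assumed. The 0.5 SD used below is also an assumption.

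**Reproducing the plan's total.** 4 strata × 1 block × 10 = 40. Each stage has two blocks, so 20 patients and 5 + 5 = 10 per arm. This matches the stated target. The text does not say outright that each block belongs to one stratum or holds 5 per arm, but this reading reproduces the totals.

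**Certain allocations in one full block.** An allocation is certain once one arm has reached m = 5. The expected number is 2m/(m+1) = 10/6 = 1.67. Enumerating all 252 orderings of a 5/5 block agrees: 1, 2, 3, 4 or 5 certain allocations occur in 140, 70, 30, 10 and 2 orderings, and the mean is 1.67.

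**Four full blocks.** 4 × 1.67 = 6.67 of 40 (16.7%). This is an average: the minimum is 4 (the last patient of each block), the median 6, the 5th to 95th percentiles 4 to 10.

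**Strata that follow the case mix.** No diabetic quota is stated. Suppose each stage recruits 20 patients, the number of diabetics is binomial, and a new block of 10 opens when one is full. Unfinished blocks then yield few certain slots:

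| Assumed diabetic share | Certain allocations of 40 | Share |
|---|---|---|
| 20% | 3.6 | 8.9% |
| 30% | 3.6 | 9.1% |
| 40% | 4.2 | 10.4% |
| 50% | 4.5 | 11.2% |

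An exact 10/10 diabetic split in both stages has a probability of at most 3% (at a 50% share: 0.176² = 0.031). If drop-outs are replaced, 40/(1 − 0.25) gives about 54 randomised, and about 6.2 to 6.5 of those 54 (11% to 12%) are certain.

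**Guessing without certainty.** Always guessing the arm that is behind is right for 6.53 of 10 allocations in a full block (65.3%), or 26.1 of 40, against 20 by chance.

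**Upper bound on bias.** If every certain slot is steered by 0.5 SD, upwards in one arm and downwards in the other, the difference shifts by (share certain) × (0.5 + 0.5). That is 0.167 × 1 = 0.17 SD with full blocks, and 0.089 to 0.112 × 1 = 0.09 to 0.11 SD with the case mix.

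**Undisclosed random blocks of 4, 6 and 8 (simulation, 10 per stratum).** About 1 of 40 allocations is certain, even to someone who knows the set of possible sizes. Tally guessing is right about 66% of the time, so no better than with blocks of 10. A stage ends exactly 10/10 about 51% of the time, and within one patient per arm about 94% of the time.

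A smaller fixed and disclosed block would be worse: 13.3 of 40 certain with blocks of 4, and 10 of 40 with blocks of 6.

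**The case against.** The strongest reply is that the opportunity is small, and much of it stands.

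- **Who is approached.** A reader might infer that the doctor freely decides whom to enrol. The documents do not say so: under Patient selection, all patients under treatment who meet the criteria are to be considered. Consent, the eligibility check and the register entry come before randomisation.
- **Lesion choice.** It follows stated criteria. Two lesions of the same stage in one patient share the same stratum and next envelope, so choosing between them can change the lesion but not the arm. Discretion is confined to judging which lesion gives better data. That judgement can set the stratum only when the two stages are level.
- **Little slack.** From Statistics, 426 × 20% × 10/12 = 71 ulcer patients are expected in 10 months, before the other criteria, against about 54 needed if losses are replaced. At about 7 candidates a month over four strata, holding a slot for a preferred patient is hard.
- **Adjustment.** The planned generalised linear models include the pre-treatment measurement and clinical covariates, which would absorb part of any steering on recorded severity.
- **Purpose.** The study calls itself a proof of concept and has no power calculation.

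These points limit the likely bias. They do not answer why the block size should be printed where the site can read it. The documents describe no varying or undisclosed block size and no central allocation.

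**Conclusion.** The point holds as a modest design improvement. A fixed block of 10 is disclosed to an unmasked site, and some allocations become certain under every scenario examined: 6.7 of 40 on average if all four blocks fill exactly, and about 3.6 to 4.5 of 40 if strata follow the case mix. The range rests on reading the scheme as one block of 5/5 per stratum, on staff keeping a tally, and on the assumed diabetic share.

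Three stronger readings are not supported. First, about 7 of 40 is not a general figure, because it needs every stratum to stop at exactly 10 and no such quota is stated. Second, 0.17 SD is not an estimate of bias. It is the top of an upper bound of 0.09 to 0.17 SD that requires every certain slot to be steered in both arms, and nothing in the documents suggests that anyone would do this. Third, varying block sizes would not make allocation unpredictable, because guessing from the tally stays at about 65% to 66%.

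**What to change.** Remove the block size and the number of blocks from the protocol and from every paper held at the site. Keep them in a sponsor randomisation file, closed to site staff, until the last patient is randomised. The protocol need only say that allocation is 1:1, in permuted blocks, stratified by stage and diabetes. This costs one changed sentence and leaves the planned balance intact. If the site already holds the current text, the deletion cannot undo the disclosure for the existing list, and a new list would be needed.

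Optionally, generate each stratum's list with undisclosed, randomly varying block sizes (for example 4, 6 and 8). This cuts certain allocations to about 1 of 40 but does not reduce tally guessing. The cost is a regenerated list and slight possible imbalance: a stage would end exactly 10/10 only about half the time, so the patient-number section should then read about 10 per arm.

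That rewording is worth making even if blocks of 10 are kept. If staff took 10 per arm per stage as exact for those randomised, each stage would act as one block of 20, with 2 × 10/11 = 1.8 certain allocations, or 3.6 of 40 over both stages.

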Patients who will not receive treatment with EmoLED and/or the provided standard dressings for more than twice within the 4-weeks observation period will be excluded from the study. Patients who have not followed any eventual therapy or medical indications prescribed by the personnel involved in the trial will also be excluded.

However, the patient has the right to withdraw from the study at any time without giving any explanation to the investigator. After the patient's discharge or abandonment of the study, the case report form is identified, scanned and archived. If a patient withdraws from the study, the Principal Investigator or their delegate records the event in the identification register and on the case report form and archives everything.

Clinical investigation monitoring plan

In order to verify that the rights, safety and well-being of enlisted patients are protected, that the reported pseudonymized data are reliable and strong and that the clinical investigation is conducted in compliance with the requirements of the current legislation, the sponsor ensures adequate monitoring of the conduct of this clinical investigation. The monitoring of the clinical investigation is entrusted to the adequately trained sponsor staff.

To guarantee the conformity with ICH/GCP guidelines, staff will be responsible for the study to be carried out in full observance of the Standard Operating Procedures, of the Protocol and other written instructions.

The main responsibilities of the staff are to ensure adherence to the Protocol, to make sure that the data are accurately and fully registered and reported and to verify the presence of the Informed Consent and that it was obtained and registered for each subject before their participation in the study.

Researchers will be contacted on a regular basis throughout the whole duration of the study to check and verify the various documents (case report forms and other relevant documents containing the original data) related to the study in order to verify the adherence to the protocol and to ensure the completeness, consistency and accuracy of the recorded data. The documents subject to verification will be identified with the progressive alphanumeric ID code.

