Early termination and suspension of clinical evaluation

In the event of suspension or early termination of the study by the promoter, taken as a safety measure due to events related to the conduct of the study that may affect the health of the patients recruited, the promoter is required to notify the Ministry of Health and the Ethics Committees involved within 90 days from the recruitment of the last patient or the early closure. In case of suspension or early termination of the study not for safety reasons, the sponsor shall justify and explain their decision. The suspended clinical trial cannot be reactivated unless a substantive amendment and the positive opinion of the Ministry of Health and the Ethics Committees have been submitted.

Statistics

Calculation of the sample number

Lack of reliable data in the scientific literature on average recovery times of decubitus ulcers (PUs), the absence of clinical experience combining blue light treatments with the therapy of this type of lesion, and the lack of reliability about any inference based on clinical studies that associate this type of treatment with other types of skin lesions, due to the different aetiologies and types of patients, do not make possible to perform a reliable calculation of the sample number. The predefined sample size was therefore set on the basis of considerations concerning the recruitment capacity of the centre involved in the project. Based on an estimate of the historical clinical activity data at the Cardiorespiratory Rehabilitation Units, at the Neuro-Motor Rehabilitation Unit and at the Acquired Severe Brain Injury Unit (UGCA), where patients will be enrolled, the percentage of patients with decubitus ulcers at the entrance is about 20%, an information that implies that compared to an average of about 426 patients/ year, in 10 months of enrollment it is possible to reach a number of 40 patients compared to a percentage of drop-out/ waste equal to about 25%. A total of 40 patients will be recruited, 20 patients with second stage PUs and 20 patients with third stage PUs. Thus, this study is intended as a "proof of concept", the results of which may be used as preliminary information to define the sample size in later studies.

Management of missing data

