Since it is a "proof of concept" study based on a limited number of patients, we will include in the study also patients who do not conclude the study according to the principle "intention to treat" and the resulting missing data will be processed through the imputation technique of the missing data *last observation carried forward - LOCF*. If the patient does not leave the study but skips one or more visits, the averages of the two adjacent visits or the last available data (LOCF) will be taken into account.

Statistical analysis

Demographic and clinical data will be presented in tables and graphs in the form of frequencies and percentages for categorical variables, mean, standard deviation, median and interquartile range for continuous variables, differentiating by reference population and treatment group. At a first analysis a qualitative comparison will be carried out between the treatment groups (improvement or not improvement), both general and differentiated for lesion of 2° and 3° stage, through the χ^2 test or Fisher's exact test for counts of less than 5. The results will be presented in contingency tables and bar charts.

A quantitative comparative statistic between the treatment groups will then be performed by comparing the outcome variables (percentage reduction of the lesion area and reduction of the PUSH index) through the non parametric test of Mann-Whitney, one of the most powerful nonparametric tests used to verify whether two independent groups belong to the same population. The Mann-Whitney test is usually applied when the assumptions to perform the parametric test are not met, which means when the distribution of the variable under study is not normal and/or the sample sizes are reduced (n 30 cases in at least one sample).

In this case, the choice to perform a non parametric analysis lies in the low sample size and therefore it is preferred to have more conservative meaningfulness values. The results will be presented in tables, with median and interquartile interval in the two groups with the relative p. value, and graphically, through box plot.

To analyse the internal and between groups time-related differences, Friedman's non-parametric test for the outcome variables will be performed.

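### The plan both excludes non-adherent randomised patients and includes non-completers by intention to treat, without saying which rule governs the primary PUSH comparison or requiring a week-4 score after exclusion

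*Combined protocol and SAP*

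**What the plan says.** The combined protocol and SAP deals with non-adherent patients in three places.

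- *Subjects discontinuation and withdrawal from the clinical investigation* has two rules. Patients who go without EmoLED "and/or the provided standard dressings for more than twice within the 4-weeks observation period will be excluded from the study". The second rule reads: "Patients who have not followed any eventual therapy or medical indications prescribed by the personnel involved in the trial will also be excluded". After the patient's "discharge or abandonment of the study, the case report form is identified, scanned and archived"; the section names no later outcome assessment.
- *Number of patients expected to enroll* sets the target at 40 evaluable patients. By that term "it is meant a patient enrolled who has respected the temporal sequence of treatments as indicated in this protocol", and "the study will continue until the number of patients required by this protocol is reached".
- *Management of missing data* says that "we will include in the study also patients who do not conclude the study according to the principle" of intention to treat, with LOCF. For a patient who stays but skips visits, it uses the mean of the adjacent visits or LOCF, with no limit on the number skipped.

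*Calculation of the sample number* drops the word evaluable: "A total of 40 patients will be recruited, 20 patients with second stage PUs and 20 patients with third stage PUs". The primary endpoint is the reduction in PUSH at the end of week 4. *Statistical analysis* compares it by the Mann-Whitney test and names no analysis set. *Bias* says that allocation cannot be masked.

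**The concern.** Both withdrawal rules act after randomisation and depend on adherence, and the second is a judgement made by staff who know the allocation. The first is also not symmetrical: a treated patient can miss EmoLED or dressings, a control patient only dressings. If excluded patients drop out of the PUSH comparison, the groups compared are no longer the groups randomised. If they stay in through LOCF alone, their week-4 outcome is assumed when it might have been observed. *Calculation of the sample number* says that the results may be used to define the sample size of later studies, so a reader of the report will need to know whom the estimate describes.

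**Working it through.** **1. Timing.** *Enrollment point* places consent and the eligibility check first, then randomisation. Exclusion for missed treatments or for not following indications during the 4 weeks therefore comes after randomisation.

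**2. Threshold.** 3 sessions a week × 4 weeks = 12 sessions. More than two missed means the third miss, or 3/12 = 25% of sessions. It can occur as early as V3, when 12 − 3 = 9 visits are still scheduled.

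**3. Three patients under the two sections.**

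| Patient | Withdrawal section | Missing-data section |
|---|---|---|
| A. Skips three visits, then attends to V12 | Excluded | Skipped visits filled in without limit; V12 observed |
| B. Attends to V12, judged not to have followed indications | Excluded | Concluded with nothing missing; the non-completer rule does not clearly apply |
| C. Third miss mid-study, removed then | Excluded | Naturally a non-completer: included by LOCF |

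For A and B the sections conflict or leave a gap, although the V12 score exists. For C they can be reconciled, but no text requires the week-4 PUSH score. The only follow-up provided after withdrawal concerns the effects of accidents (*Safety follow-up of subjects withdrawn from the Study or who have completed the same*). LOCF then carries forward an earlier score, possibly the baseline.

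**4. The plan's accrual figure.** Inputs from *Calculation of the sample number*: 426 patients a year, 20% with ulcers, 10 months, 25% drop-out or waste.

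- 426 × 10/12 × 0.20 = 71 patients with ulcers.
- 71 × (1 − 0.25) = 53.25, above 40, so 40 is reachable as stated.

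The text does not say whether the 25% falls before or after randomisation, so these figures do not settle what 40 counts.

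**5. Size of the analysis set.** Assume that the 25% falls after randomisation and consists of patients excluded as non-adherent.

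| 40 means | Randomised | All randomised analysed | Only evaluable analysed |
|---|---|---|---|
| Randomised | 40 | 40 | 40 × 0.75 = 30 |
| Evaluable | 40/0.75 = 53.3, so 54 | 54 | 40 |

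If the 25% falls before randomisation, 30 and 54 do not arise.

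**6. Illustration of leaving excluded patients out.** None of these inputs is in the documents. Assume no true effect, a normal outcome, the same number excluded in each arm, random exclusion among controls, and exclusion among treated patients correlated with poor outcome. The table gives the simulated two-sided Mann-Whitney type I error at 0.05 (8,000 runs each; the plan does not state sidedness).

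| Per arm: randomised / excluded | Correlation 0.25 | 0.50 | 0.75 |
|---|---|---|---|
| 20 / 2 | 5% | 6% | 7% |
| 20 / 5 | 6% | 8% | 14% |
| 27 / 7 | 6% | 10% | 18% |

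With everyone kept, or with random exclusion in both arms, it is 4% to 5%. With 7 of 27 excluded, the spurious difference is about 0.11, 0.21 and 0.31 SD. If the assumed correlation is reversed, so is the direction. The table shows that the effect can be negligible or material; it does not estimate it for this trial.

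**The case against.** The best defence is that the missing-data section already answers the question. It does more than name intention to treat: it includes patients who do not conclude the study, says how their data are filled in, and sets no limit on skipped visits. A patient removed mid-study is naturally a non-completer. That stands for patient C and narrows the point. It does not settle A or B, and it does not require a week-4 score for C.

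The definition of evaluable appears only under recruitment, and the statistical sections never use it. A reader might infer that the primary comparison is confined to adherent patients; the documents do not say that. Recruiting until 40 patients have adhered is compatible with analysing everyone randomised, but then more than 40 may be randomised, and the plan should say so.

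A reader might also take the archiving sentence to mean that data collection closes when staff exclude a patient. It speaks of discharge or abandonment and does not say so. What stands is that no later outcome visit is named. Exits and their reasons must be entered in the enrolment register (*Quality assurance, control procedures, data management and record keeping*), so exclusions will at least be traceable.

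Two further inferences fail. The 53 in step 4 should not be set against the 54 in step 5: the first is already net of the 25%, and the second applies it again. Nor do unmasked allocation and the extra route to exclusion in the treated arm show a bias in favour of the device, because the documents give neither an exclusion rate nor any link between exclusion and outcome.

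Finally, this is a proof of concept without a power calculation. That lowers the stakes, but in a small trial each exclusion also counts for more.

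**Conclusion.** The point holds as an unresolved conflict between sections, not as an absence of intention to treat. The withdrawal section excludes on adherence, the recruitment target counts adherent patients, and the missing-data section includes non-completers. No text says which rule governs the primary PUSH comparison, and none requires a week-4 score after exclusion. The gap is clearest for a patient who reaches V12 having met an exclusion criterion.

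The size and direction of any bias cannot be derived from the documents. The analysis set could be 30, 40 or 54 patients, but only if the 25% loss falls after randomisation and reflects non-adherence. The type I error figures rest wholly on assumed exclusion patterns.

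This should be fixed before analysis. Confidence is medium, because a sympathetic reading of the missing-data section covers part of the problem.

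**What to change.** - In *Management of missing data* or *Statistical analysis*, state that the primary PUSH comparison includes all randomised patients in their allocated arm, except where data were destroyed after withdrawal of consent to data processing.
- Reconcile the withdrawal section with this, so that meeting its criteria does not remove a patient from that analysis. Whether treatment continues is a clinical matter for the sponsor to reconcile.
- Collect the remaining scheduled PUSH scores and photographs to V12 where the patient is reachable and consents. Use the missing-data rule only when V12 cannot be obtained.
- Use the evaluable set only for a secondary per-protocol analysis, with a definition consistent with the withdrawal criteria.
- State whether 40 means randomised, as *Calculation of the sample number* suggests, or evaluable, as *Number of patients expected to enroll* says.

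The cost is small: wording in four sections, and a few further scheduled assessments in patients who stop treatment, some of whom may not be reachable.
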